4.4.2. Analysis of Key Secondary Efficacy Endpoints

4.4.2.1. Adjudicated sVOE-CR

Analysis for Group C

One of the key secondary efficacy endpoints, sVOE-CR, is defined as the complete resolution of adjudicated sVOE between 6 months and 18 months after drug product infusion. The analysis population can be found in [Table 4](#).

Responders of sVOE-CR are subjects who do not have any adjudicated sVOEs between 6 months and 18 months (i.e., 183 to 548 days) after drug product infusion.

Non-Responders of sVOE-CR are subjects who meet any of the following criteria:

- Has ≥ 1 adjudicated sVOE between 6 months and 18 months after drug product infusion. If a subject has an adjudicated sVOE that occurs before 183 days but ends after 183 days after drug product infusion, the subject is considered as a non-responder.
- Discontinues from the study on or before 18 months follow-up post-drug product infusion

The percentage of subjects who achieve sVOE-CR will be presented with a 2-sided exact 95% CI using Clopper-Pearson method for the binomial distribution. The success criterion will be at least 24 out of 35 subjects achieving sVOE-CR (i.e., rate of sVOE-CR $\geq 69\%$), giving a lower bound of the 95% CI greater than 50%, if exactly 35 TPVOE subjects in Group C. If there are fewer than 35 subjects in the analysis population, with the same assumptions such as the null hypothesis as 50% and alternative hypothesis as 85%, the power and success criterion can be found in [Appendix 6.3, Table 13](#).

Supplementary Analyses for Group C

The following Supplementary analyses, but not limited to, will be conducted:

Analysis Population	Supplementary Analysis
TPVOE ^[1]	The analysis will be repeated using protocol sVOE instead of adjudicated sVOE.
TPVOE ^[1]	Non-Responders of sVOE-CR are subjects who meet any of the following criteria: 
• Has ≥ 1 adjudicated sVOE between 6 months and 18 months after drug product infusion. If a subject has an adjudicated sVOE that occurs before 183 days but ends after 183 days after drug product infusion, the subject is considered as a non-responder.• Has any death related to VOE (adjudicated by independent committee) or drug product/study procedure (assessed by investigator) on or before 18 months post-drug product infusion. Subjects in the TPVOE who don't meet any of the non-responder criteria above will be excluded from the analysis if they discontinued from the study on or before reaching 18 months post-drug product infusion.

If there is no death or discontinuation on or before 18 months post-drug product infusion, the results will be the same as for the primary analysis of sVOE-CR, so this supplementary analysis will not be performed in this case.

^[1] If an interim analysis is performed, subjects should also have or would have at least 18 months of follow up post-drug product infusion.

Analysis for Groups A and B

The number and percentage of subjects achieving sVOE-CR will be reported by group for Groups A and B subjects in TPVOE at final analysis, or in TPVOE who have or would have 18 months follow-up at interim analysis. No 95% CI will be presented given the relatively small sample size.

4.4.2.2. Globin Response

Analysis for Group C

The key secondary efficacy endpoint, Globin Response, defined as meeting the following criteria for a continuous period of at least 6 months after drug product infusion (starting ≥ 60 days after last pRBC transfusion):

- a. Weighted average HbA^{T87Q} percentage of non-transfused total Hb $\geq 30\%$
AND
- b. Weighted average non-transfused total Hb increase of ≥ 3 g/dL compared to baseline total Hb, OR weighted average non-transfused total Hb ≥ 10 g/dL

The detailed definition of Globin Response can be found in [Section 1.2.6.2](#). The analysis population can be found in [Table 4](#).

The weighted average HbA^{T87Q} percentage of non-transfused total Hb is defined as

$$[(t_1 - t_0) \times \frac{(p_0 + p_1)}{2} + (t_2 - t_1) \times \frac{(p_1 + p_2)}{2} + \dots + (t_k - t_{k-1}) \times \frac{(p_{k-1} + p_k)}{2}] / (t_k - t_0)$$

Where

- t_0 represents the time of the first HbA^{T87Q} assessment post-drug product infusion and there is no pRBC transfusion in the previous 60 days, and t_1, t_2, \dots, t_k represent continuous time points for HbA^{T87Q} assessments after t_0 and no pRBC transfusion occurs between these timepoints.
- $p_0, p_1, p_2, \dots, p_k$ represent the HbA^{T87Q} percentage to non-transfused total Hb at each of these time points
- $t_k - t_0$ must be at least 6 months, which is 183 days ([with exception below](#)).

This calculation is invariant to the metric used for the time points, e.g., calendar dates or days from drug product infusion, since the consecutive differences in times would always be measured in number of days.

After drug product infusion, HbA^{T87Q} will be assessed at Month 1, 2, 3, 4.5, 6, and then every 3 months through Month 24. In the situation where there are three consecutive scheduled HbA^{T87Q} assessments in a 6-month period of time (i.e., every 3-month) and scheduled Hb^{AT87Q} assessments are within visit window but are less than 6 months apart, then the ≥ 6 months requirement will not be needed, however, the requirement of starting ≥ 60 days after the last pRBC transfusion still needs to be met. Scheduled visits for assessments are defined in [Appendix 6.2, Table 12](#). The weighted average may be considered as an average AUC calculation for HbA^{T87Q} percentage. Note that the weighted non-transfused total Hb can be calculated in a similar way.

A TP subject will be considered as a non-responder if the subject does not achieve Globin Response before discontinuing from the study.

The percentage of subjects who achieve Globin Response will be presented with a 2-sided exact 95% CI using the Clopper-Pearson method for the binomial distribution. The success criterion at

the final analysis will be at least 24 out of 41 subjects achieving Globin Response (i.e., rate of Globin Response $\geq 59\%$), giving a lower bound of the 95% CI greater than 40%, if exactly 41 TP subjects in Group C. If there are fewer than 41 subjects in the analysis population, with the same assumptions such as the null hypothesis as 40% and alternative hypothesis as 70%, the power and success criterion can be found in [Appendix 6.3, Table 13](#).

Analysis for Groups A and B

The number and percentage of subjects reaching Globin Response will be reported by group for Groups A and B subjects in TP at final analysis.

No 95% CI will be presented given the relatively small sample size.

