7.4.4.2.2. Analysis of Globin Response

This key secondary endpoint of Globin Response will be tested against the null hypothesis of 40% using a 1-sided exact binomial test. The number and percentage of subjects reaching this key secondary endpoint will be presented. The associated 2-sided exact 95% confidence interval will be provided. The endpoint will be analyzed in the TP for Group C subjects.

Globin Response is defined as meeting the following criteria for a continuous period of at least 6 months after drug product infusion:

- Weighted average HbA^{T87Q} percentage of non-transfused total Hb $\geq 30\%$; AND
- Weighted average non-transfused total Hb increase of ≥ 3 g/dL compared to baseline total Hb OR weighted average non-transfused total Hb ≥ 10 g/dL.

The estimand examines the proportion of subjects achieving Globin Response for a continuous period of at least 6 months after drug product infusion starting \geq 60 days after the last pRBC transfusion among all subjects who receive bb1111.

Subjects must meet these criteria for a continuous period of \geq 6 months after drug product infusion (starting \geq 60 days after last pRBC transfusion).

The weighted average HbA^{T87Q} percentage is defined as:

$$[(t_1-t_0) \times ((p_0+p_1)/2) + (t_2-t_1) \times ((p_1+p_2)/2) + \dots + (t_k-t_{k-1}) \times ((p_{k-1}+p_k)/2)]/(t_k-t_0),$$

where

- t_0 represents the time of the first HbA^{T87Q} assessment where there is no pRBC transfusion in the previous 60 days, and t_1, t_2, \dots, t_k represent continuous time points for HbA^{T87Q} assessments after t_0 where no pRBC transfusion occurs between these timepoints.
- $p_0, p_1, p_2, \dots, p_k$ represent the HbA^{T87Q} percentage at each of these time points.
- t_k-t_0 must be at least 6 months.

HbA^{T87Q} is assessed every 3 months starting from Month 3 after drug product infusion. In the event that there are 3 consecutive scheduled HbA^{T87Q} assessments that are within visit window but are less than 6 months apart, the \geq 6-month requirement will not be needed. The weighted average may be considered as an average AUC calculation for HbA^{T87Q} percentage.

Note that the weighted total Hb can be calculated in a similar way.

Sensitivity and/or supplementary analyses for the key secondary endpoints will be detailed in the SAP.

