3. GENERAL STATISTICAL METHODS

3.1. Sample Size Justification

The sample sizes for Groups A and B are not determined by formal statistical methods.

Approximately 41 subjects will be enrolled in Group C with approximately 35 subjects meeting the severe VOE criteria as defined in Inclusion Criterion #3.1.

- For the primary endpoint, VOE-CR: assuming 80% of Group C subjects in the TPVOE will meet the primary efficacy endpoint, 35 subjects will provide more than 99% power to reject the null hypothesis of 40% at 1-sided alpha of 0.025, using the Exact Test per EAST® (Version 6). The success criterion is 60% (21 out of 35) of subjects meeting the primary efficacy endpoint, if exactly 35 subjects with at least 4 VOEs in the 24 months prior to ICF are enrolled and receive drug product in Group C.
- For the key secondary endpoint, sVOE-CR: assuming 85% of Group C subjects in the TPVOE will meet the primary efficacy endpoint under the alternative hypothesis, 35 subjects will provide more than 99% power to reject the null hypothesis of 50% at 1-sided alpha of 0.025, using the Exact Test per EAST® (Version 6). The success criterion is 69% (24 out of 35) of subjects meeting the key secondary endpoint, if exactly 35 subjects who have at least 4 VOEs in the 24 months prior to ICF are enrolled and received drug product in Group C.
- For the key secondary endpoint, Globin Response: assuming 70% of Group C subjects in the TP will meet the key secondary efficacy endpoint under the alternative hypothesis, 41 subjects will provide approximately 96% power to reject the null hypothesis of 40% at 1-sided alpha of 0.025, using the Exact Test per EAST® (Version 6). The success criterion is 59% (24 out of 41) of subjects meeting the key secondary efficacy endpoint, if exactly 41 subjects are enrolled and received drug product in Group C.

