Endpoint (variable)	Complete resolution of adjudicated VOEs between 6 months and 18 months after drug product infusion (i.e., VOE-CR)	Complete resolution of adjudicated severe VOEs between 6 months and 18 months after drug product infusion (i.e., sVOE-CR)	Globin Response, as defined in Section 1.2.6.2
Intercurrent event (ICE)	Discontinues from the study before reaching the 18th month follow-up post-drug product infusion will be considered as a non-responder.	Discontinues from the study before reaching the 18th month follow-up post-drug product infusion will be considered as a non-responder.	Discontinues from the study before achieving Globin Response will be considered as a non-responder. pRBC transfusion is considered an intercurrent event. Starting \geq 60 days after last pRBC transfusion, a subject should meet Globin Response for a continuous period of at least 6 months after drug product infusion.
Population-level Summary	Proportion of subjects achieving VOE-CR among the subjects who are in the analysis population	Proportion of subjects achieving sVOE-CR among the subjects who are in the analysis population	Proportion of subjects achieving Globin Response among subjects who are in the analysis population

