4.4.3.2. Hematologic Endpoints

All hematologic endpoints indicated below will be based on subjects in the TP and summary tables will be presented by group.

- **Weighted average of the following at Month 6, 12, 18 and 24:**
 - non-transfused total Hb
 - HbS percentage of non-transfused total Hb
 - HbS percentage of non-transfused total Hb $\leq 70\%$, $\leq 60\%$, $\leq 50\%$
 - HbA^{T87Q} percentage of non-transfused total Hb
 - non-HbS percentage of non-transfused total Hb

Descriptive summary statistics or frequency distribution of the weighted average of the endpoints above at Month 6, 12, 18 and 24 will be provided. Data starting ≥ 60 days after the last pRBC transfusion will be utilized. The weighted average will be based on the assessments obtained up to an approximately 6-month period and can be calculated in a similar way as the weighted total Hb in the Globin Response in [Section 4.4.2](#). For example, for the weighted average at Month 6, all assessments post-drug product infusion up to Month 6 Visit will be used; for the weighted average at Month 12, all assessments obtained between Month 6 Visit and Month 12 Visit will be utilized for the calculation.

- **Assessment of the following over time:**
 - non-transfused total Hb
 - HbS percentage of non-transfused total Hb
 - HbA^{T87Q} percentage of non-transfused total Hb
 - non-HbS percentage of non-transfused total Hb

Descriptive summary statistics will be provided for the endpoints above over time per SOE. If there are multiple assessments within the same SOE time window, the average values will be presented in the tables. Change from baseline in non-transfused total Hb will also be presented, where baseline total Hb (as defined in [Section 1.2.6.2](#)) will serve as the baseline for non-transfused total Hb.

- **Hemolysis markers, markers of iron stores, and markers for stress erythropoiesis**

Descriptive summary statistics will be provided for these biomarkers over time and change from baseline will also be presented. Baseline is defined the first assessment on or after Informed Consent but before initiation of stem cell collection.

- **Change from baseline in annualized frequency and volume of pRBC transfusions between 6 months and 24 months after drug product infusion**

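### Globin Response start rules are not reconciled: the formula fixes t0 at the first transfusion-free assessment with no restart, while the definition and estimand count from the last transfusion

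*SAP*

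**What the plan says.** Two start rules stand side by side.

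- **Formula rule.** SAP 4.4.2.2 sets t0 at the first HbA^T87Q "assessment post-drug product infusion and there is no pRBC transfusion in the previous 60 days". Later time points count only if they follow t0 "and no pRBC transfusion occurs between these timepoints". Protocol 7.4.4.2.2 has the same construction, with t0 at the first "assessment where there is no pRBC transfusion in the previous 60 days". Neither text provides a second t0.
- **Definition rule.** The endpoint definition that opens SAP 4.4.2.2, its short-window exception and the estimand in Protocol 7.4.4.2.2 all start the 6-month period at least 60 days after the last pRBC transfusion. SAP Table 4 names pRBC transfusion as an intercurrent event and handles it the same way: starting at least 60 "days after last pRBC transfusion, a subject should meet Globin Response for a continuous period of at least 6 months".

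The minimum window is 183 days, or three consecutive 3-monthly scheduled visits if these fall slightly short. SAP 4.4.3.2 applies similar wording to the Month 6, 12, 18 and 24 weighted averages: data starting at least 60 "days after the last pRBC transfusion will be utilized".

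Neither document says whether *last* means the final transfusion on study or the most recent one before the window. Neither says whether t0 may restart, or whether a later transfusion cancels a response already reached. SAP 5.1 reports no change from the protocol, so neither document resolves the other.

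**The concern.** Globin Response is a key secondary endpoint with a numeric success rule. Transfusion after engraftment is foreseen: Protocol 3.1 provides for transfusion needs beyond 6 months, and transfusions between Months 6 and 24 are themselves a secondary endpoint. A subject transfused again after t0 is therefore a realistic case, and it is the case in which the two rules can part.

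Under the formula, a single transfusion soon after t0 breaks the only window that the subject is given. Under the definition, the same subject starts a new window and can still respond. Classification then depends on which sentence the programmer follows. Response status also carries into SAP 4.4.3.1: Duration and Month 24 Globin Response both run from t0, and the Month 24 denominator is the subjects who achieved the response.

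**Working it through.** **The plan's own figure.** Inputs from SAP 3.1: "41 subjects will provide approximately 96% power to reject the null hypothesis of 40% at 1-sided alpha of 0.025", "assuming 70% of Group C subjects in the TP will meet the key secondary efficacy endpoint under the alternative hypothesis", and "The success criterion is 59% (24 out of 41) of subjects meeting the key secondary efficacy endpoint". With X ~ Binomial(41, p):

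- P(X ≥ 24 | p = 0.40) = 0.0126, and P(X ≥ 24 | p = 0.70) = 0.9586, matching the stated 96%.
- P(X ≥ 23 | p = 0.40) = 0.0270, above 0.025, so 24 is the correct minimum.

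All seven Globin Response rows of SAP Table 13 (n = 41 to 35) reproduce.

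**Classification check.** Visit days are the nominal ones in SAP Table 12: 30, 60, 90, 135, 180, then every 90 days to 720. Assumptions: transfusions around transplant end on Day L, one isolated transfusion follows on Day d, and the haemoglobin criteria are met at every assessment.

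For L = 30:

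1. First t0: 30 + 60 = 90, so Day 90.
2. Formula: the first complete window is Days 90, 180 and 270. It spans 180 days, under 183, but passes by the three-visit exception. A transfusion on Day 91-270 breaks it. From Day 271 it is already complete.
3. Definition: a new window opens at the first visit on or after d + 60. For d = 270 this is 330, so Day 360, leaving 720 − 360 = 360 days: responder.
4. Definition with *last* read as final: three visits must remain (Days 540, 630, 720), so d + 60 ≤ 540 and d ≤ 480. For d = 481 only Days 630 and 720 remain: non-responder. Calendar arithmetic without visits would give 731 − 183 − 60 = Day 488; the visit schedule brings it to Day 480.

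| L | First t0 | Formula non-responder, definition responder | Responder under both | Formula responder, *final* reading non-responder |
|---|---|---|---|---|
| 20 | 90 | 91-270 | 81-90, 271-480 | after 480 |
| 30 | 90 | 91-270 | 271-480 | after 480 |
| 60 | 135 | 136-360 | 121-135, 361-480 | after 480 |
| 100 | 180 | 181-360 | 161-180, 361-480 | after 480 |

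(For L = 20, 60 and 100, a transfusion in the earlier agreeing span comes on or before the t0 shown, so t0 itself moves later.)

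The third column holds whether *last* means final or most recent, because only one transfusion follows. If *last* means most recent and t0 may restart, the subject is a responder on every day tested.

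**Weight of one subject.** SAP Table 1 lists 36 Group C infusions, so one subject is 1/36 = 2.8 percentage points. At n = 41 it is 1/41 = 2.4 points.

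| Responders | Exact one-sided p against 40% | Lower 95% limit |
|---|---|---|
| 24/41 | 0.0126 | 0.4211 |
| 23/41 | 0.0270 | 0.3975 |
| 21/36 | 0.0200 | 0.4076 |
| 20/36 | 0.0426 | 0.3810 |

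**The case against.** The best defence is that *last* means most recent. In the haemoglobin footnote of SAP 1.2.6.2 the word is attached to a sample, so it sensibly means the transfusion before that sample. The 60-day look-back and the ban on transfusion within the window would then only put *last* into operation. The definition also asks for a continuous period, not one unique period, and SAP 4.4.3.1 ties t0 to the date on which the response begins.

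Much of this stands. A reader might infer that the rules are flatly incompatible; the documents show an undefined term, not a proven contradiction. Usage is mixed, since footnote 13 to the follow-up schedule in the protocol uses *last* for final, though about antibody screening. But the defence does not close the gap: even with *last* as most recent, the formula still fixes t0 at the first qualifying assessment and states no restart.

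Three stronger inferences are not supported:

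- *The rules agree only if the subject is never transfused again.* With L = 30 and a transfusion on Day 370, the formula window is Day 90-360 (270 days). The later window is Day 450-720 (also 270 days). The subject responds under both.
- *A late transfusion erases a response already held.* This needs *last* to mean final. It fits poorly with Table 4 and SAP 4.4.2.2, which treat the response as something achieved, and with SAP 4.4.3.1, which measures persistence separately.
- *A late transfusion deletes all earlier data from the weighted averages.* SAP 4.4.3.2 builds each average from its own roughly 6-month block, so this is a strained reading.

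Nor do the documents show that anyone has chosen between readings with outcomes in view.

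**Conclusion.** The point holds in a limited form. The formula as written gives a non-responder, and the definition and Table 4 can give a responder, for a subject transfused again soon after t0: Day 91-270 if earlier transfusions end on Day 30, and up to Day 360 if they end on Day 60 or 100. This does not depend on the meaning of *last*. The opposite conflict after about Day 480 does, and is the weaker half. In between, the two rules agree.

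The stated power and success thresholds are unaffected; what is open is who counts as a responder. How many subjects had such a transfusion is not in the documents, so the effect on the rate cannot be sized beyond 2.8 points per subject at n = 36. One subject changes the conclusion only at the success boundary. The day ranges rest on nominal visits, haemoglobin criteria always met, and a single isolated later transfusion. It should be corrected, because a stated derivation rule can misclassify subjects on a key secondary endpoint and the correction is cheap.

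**What to change.** In SAP 4.4.2.2, SAP Table 4 and Protocol 7.4.4.2.2, state one rule:

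- t0 may be any post-infusion assessment at least 60 days after the most recent preceding pRBC transfusion, and it restarts after each transfusion.
- A subject is a responder if any transfusion-free interval meeting the 6-month rule, or its three-visit exception, satisfies both haemoglobin criteria.
- A transfusion after that affects only Duration and Month 24 Globin Response, not the achieved response.

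In SAP 4.4.3.2, state that only assessments within 60 days after a transfusion are left out of the 6-monthly weighted averages. List the subjects whose status differs between the two current readings.

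The cost is a few sentences and a small change to the derivation program, with no new data. If the program already works this way, only the wording is needed. The change concerns endpoint derivation alone and has no bearing on how transfusions are managed.

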4.4.3. Analysis of Other Efficacy Endpoints

4.4.3.1. Characterization of Globin Response (only for Group C subjects who have achieved Globin Response)

- Proportion of subjects who meet the definition of Globin Response at Month 24**
 - The numerator is the number of subjects who continuously meet Globin Response criteria from the first date of Globin Response initiating (t_0) to Month 24 visit of HPLC assessment
 - The denominator is the number of subjects who have achieved Globin Response.

If after achieving Globin Response, a subject discontinues from the study before having the Month 24 visit of HPLC assessment, then the subject will also be considered as a non-responder.

The percentage of subjects who maintain Globin Response at Month 24 will be presented with a 2-sided 95% CI using Clopper-Pearson method.

Supplementary Analyses

The following Supplementary analyses will be conducted:

Analysis Population	Supplementary Analysis
TP	
The primary analysis will be repeated, but after achieving Globin Response, subjects with death or discontinuation unrelated to the drug product will be considered as not evaluable.
 
If after achieving Globin Response but before having the Month 24 visit of HPLC assessment, there is death or discontinuation related to the drug product, then the subject will be considered as a non-responder.

- Duration of Globin Response**

Duration of Globin Response is from the first date of Globin Response initiating (t_0) to the date of last HPLC assessment such that the weighted average of HbA^{T87Q} percentage of non-transfused total Hb, non-transfused total Hb, and non-transfused total Hb increase from the baseline total Hb (if baseline total Hb is available) continuously meet Globin Response criteria

during this time period. Duration of Globin Response (in months) and these weighted average values during Globin Response will be summarized.

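### Globin Response at Month 24 and its Duration rest on an average anchored at t0 with no maximum span, so a subject who lost the response in the last 6 months can still be counted as maintaining it

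*SAP*

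**What the plan says.** SAP 4.4.3.1 has two endpoints for Group C subjects who achieved Globin Response.

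- **Month 24 status.** "The numerator is the number of subjects who continuously meet Globin Response criteria from the first date of Globin Response initiating" to the Month 24 HPLC assessment. "The denominator is the number of subjects who have achieved Globin Response". A responder who discontinues before that assessment counts as a non-responder. The percentage is reported with a Clopper-Pearson 95% interval.
- **Duration.** "Duration of Globin Response is from the first date of Globin Response initiating", and it extends "to the date of last HPLC assessment such that the weighted average of HbA^{T87Q} percentage of non-transfused total Hb", together with the total Hb averages, still meets the criteria.

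The criteria come from SAP 4.4.2.2: average HbA-T87Q of at least 30%, and average non-transfused total Hb either at least 10 g/dL or at least 3 g/dL above baseline. That section has the only averaging formula, a trapezoidal average from t0 to tk divided by tk minus t0; Protocol 7.4.4.2.2 has the same one. There t0, the anchor, "represents the time of the first HbA^{T87Q} assessment post-drug product infusion and there is no pRBC transfusion in the previous 60 days". The span "must be at least 6 months, which is 183 days", with an exception when three consecutive scheduled assessments are within visit window but less than 6 months apart. No upper limit is given. Between t0 and tk, "no pRBC transfusion occurs between these timepoints".

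SAP 4.4.3.2 does restrict the window for its descriptive averages at Months 6, 12, 18 and 24: "for the weighted average at Month 12, all assessments obtained between Month 6 Visit and Month 12 Visit will be utilized for the calculation". SAP 4.4.3.1 has no such restriction.

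**The concern.** These two endpoints exist to show whether the response lasts after a single dose. Status at Month 24 should therefore depend on values near Month 24. An average that starts at t0 and has no maximum length spans 21 months by Month 24 if t0 is at Month 3, so the last 6 months carry less than a third of the weight. A late fall below the criteria can be outweighed by the earlier plateau.

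At stake are the reported percentage maintaining response and the reported duration. The denominator is small: SAP Table 1 lists 36 infused Group C subjects, so with at most 36 responders one reclassified subject moves the percentage by at least 1/36 = 2.8 points.

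**Working it through.** **The plan's own figure.** The documents give no expected value for either endpoint. The nearest figure is for the parent Globin Response test (SAP 3.1): 24 of 41, 40% versus 70%, one-sided 0.025, about 96% power. The exact binomial gives power 0.9586 and type I error 0.0126; a cut-off of 23 would give 0.0270. The stated figure reproduces, and nothing below changes it.

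**Inputs.** The formula and criteria are those of SAP 4.4.2.2. Scheduled days are 90, 135, 180, then every 90 days to 720 (SAP Table 12). The patient profiles are assumptions, because the documents give none.

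**Formula.** Average = sum of (t_i − t_{i−1}) × (p_{i−1} + p_i)/2, divided by (t_k − t_0). It is computed from t0 to Day 720 (cumulative) and over Days 540 to 720 (trailing).

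*Profile A: HbA-T87Q 45% through Month 15, then 15% at Months 18, 21 and 24.*
- t0 at Day 90: (360×45 + 90×30 + 180×15)/630 = 21600/630 = 34.3%.
- t0 at Day 180: (270×45 + 90×30 + 180×15)/540 = 17550/540 = 32.5%.
- Trailing: 15%.

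*Hb alongside A: 11.5 g/dL through Month 15, then 8.0, t0 at Day 90.*
- Cumulative: (360×11.5 + 90×9.75 + 180×8.0)/630 = 6457.5/630 = 10.25 g/dL, which passes the 10 g/dL limb.
- Trailing: 8.0 g/dL, which also fails the 3 g/dL limb unless baseline is 5.0 g/dL or lower.

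*Profile B: 35% through Month 18, then 20% at Months 21 and 24, t0 at Day 180.*
- Cumulative: (360×35 + 90×27.5 + 90×20)/540 = 16875/540 = 31.25%.
- Trailing: (90×27.5 + 90×20)/180 = 23.75%.

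*Profile C: 32% through Month 18, then 20%, t0 at Day 180.*
- Cumulative: (360×32 + 90×26 + 90×20)/540 = 15660/540 = 29.0%.
- Trailing: (90×26 + 90×20)/180 = 23.0%.

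| Profile | t0 | Cumulative | Trailing | 30% criterion |
|---|---|---|---|---|
| A | Month 3 | 34.3% | 15% | passes / fails |
| A | Month 6 | 32.5% | 15% | passes / fails |
| B | Month 6 | 31.25% | 23.75% | passes / fails |
| B | Month 12 | 29.38% | 23.75% | fails / fails |
| C | Month 6 | 29.0% | 23.0% | fails / fails |

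**Does checking every visit help?** Not if the average checked is cumulative. In profile A with t0 at Day 90, the running value is 18900/450 = 42.0% at Day 540, 20250/540 = 37.5% at Day 630 and 34.3% at Day 720. All pass.

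**Duration in profile A, t0 at Day 90.** Judged on HbA-T87Q and the Hb profile above, the cumulative rule credits Day 90 to Day 720: 630 days, or 20.7 months at 30.4375 days per month. The trailing HbA-T87Q average is (90×45 + 90×30)/180 = 37.5% at Day 540 and (90×30 + 90×15)/180 = 22.5% at Day 630. The trailing Hb average at Day 540 is (90×11.5 + 90×9.75)/180 = 10.6 g/dL. Duration therefore ends at Day 540: 450 days, or 14.8 months.

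**How far can the late value fall?** With t0 at Month 6, a plateau p through Month 18 and a late value q at Months 21 and 24, the cumulative average still passes if q ≥ (30×540 − 405p)/135. That is 24% for p = 32, 15% for p = 35 and 0% for p = 40. The trailing rule needs q ≥ (30×180 − 45p)/135: 29.3%, 28.3% and 26.7%.

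**The case against.** The SAP never calls the average cumulative. *Continuously* could mean that every successive qualifying 6-month period must meet the criteria, which would catch the loss. This stands as a statement about the text, but it does not remove the problem. The only formula supplied starts at t0, and SAP 4.4.3.1 also summarises the weighted averages during Globin Response, which fits a whole-period average. At best, two programmers could derive different Month 24 rates and durations from the same data.

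A reader might infer that any subject who loses the response late is still counted. The documents do not support that. The result depends on plateau, t0 and depth of loss: profile C fails on either rule, and profile B fails with t0 at Month 12. A pRBC transfusion breaks the run, and discontinuation before the Month 24 HPLC assessment is non-response.

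A reader might also infer that the loss would be hidden. It would not. SAP 4.4.3.2 reports averages over about 6 months at Month 24 and values over time, SAP 4.5 plots each Hb fraction by subject, and SAP 4.4 provides listings for all efficacy endpoints. These do not, however, correct the responder count or the duration.

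**Conclusion.** The point holds as a possibility created by the rule. On the plain reading of SAP 4.4.3.1 with 4.4.2.2, a subject whose last 6 months are below the criteria, without transfusion or discontinuation, can be counted as maintaining response at Month 24 and credited with full duration. In the assumed profiles the cumulative HbA-T87Q average exceeds the trailing one by 7.5 points (31.25% against 23.75%) to 19.3 points (34.3% against 15%), and in profile A duration is 20.7 rather than 14.8 months.

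It does not follow that durability in this trial is overstated. The documents contain no late-loss data, and the profiles are illustrative. Both endpoints are descriptive secondary endpoints among responders. The primary endpoint and the 24-of-41 Globin Response test are untouched. The SAP should be changed because the rule can give the wrong answer to the question these endpoints ask.

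**What to change.** In SAP 4.4.3.1, keep the continuity requirement and define it. A subject continuously meets Globin Response if both criteria are met by the weighted average over each successive trailing period of about 6 months from t0, including Month 18 to Month 24, with no intervening pRBC transfusion. Carry over the visit-window exception of 4.4.2.2, because the target days for Months 18 and 24 (540 and 720) are only 180 days apart, under the 183-day minimum. End Duration at the last assessment whose trailing average meets both criteria, or at a transfusion if that is earlier. Report the cumulative version as supplementary.

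Testing the Month 18 to Month 24 window alone would not be enough: it would drop continuity and count a subject who lost the response mid-study and regained it.

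The cost is SAP wording and some programming. No new data are needed, and similar windowing is already required for 4.4.3.2. The downsides are that reported durability may be lower and that windowed averages, resting on fewer assessments, are somewhat noisier.
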